5.4.7 Tissue, Plasma, and Whole Blood Samples

Tissue and plasma samples (for mutational detection) are not required for patients in Phase 1 of the study.

5.4.7.1 Tissue and Whole Blood Samples

Tissue (Phase 2 Only): A tissue sample is required prior to Cycle 1, Day 1. If an archival tissue sample is not available, a tumor biopsy will be required.

The tissue from the biopsy will be processed according to site procedures into a Formalin-Fixed Paraffin-Embedded (FFPE) block. A tissue sample collected at disease progression is optional. Embedded tumor tissue will be shipped to the central laboratory and stored at room temperature. DNA and/or RNA will be extracted from FFPE samples and subjected NGS mutational detection analysis (companion diagnostic development and resistance mechanism study).

5.4.7.2 Whole Blood Samples

- **Phase 1 and Phase 2:** Whole blood samples (4 mL) will be collected once at Screening for CYP2D6 genotyping (metabolic profile analysis). Whole blood samples will be shipped at room temperature.
- **Phase 2 only:** Whole blood samples (20 mL) will be drawn for plasma ctDNA analysis at Screening and when the patient progresses (collecting a sample at progression is optional but is highly encouraged). Blood samples will be processed at the site and shipped to the lab for storage at -70°C until ready for testing (companion diagnostic development and resistance mechanism study). Blood samples will also be collected on Day 1 of Cycles 2 and 3 and then every 8 weeks thereafter in order to correlate pozotinib concentrations with ctDNA and efficacy.

5.4.7.3 Sample Retention

All samples will be banked at the lab for 5 years or for the duration that is compliant with local law. After this time, if no further analysis is planned, the Sponsor will request that the samples be destroyed as per local storage procedures.

Banked samples will not be returned to the patient for any reason, even if the patient withdraws consent during the term of the study or after the patient withdraws from the study. These samples will be destroyed as described above or upon the request for destruction from the subject. In addition, even if the patient withdraws consent to use/store the optional samples while participating in this study, the patient can continue participating in this study if they wish.

Genetic testing results will not be provided to patients unless requested by patients' physicians.

5.4.8 Pharmacokinetics

Phase 1: The pharmacokinetics of pozotinib and M1 and M2 metabolites evaluated. Patient will have intensive PK blood samples drawn (4 mL whole blood each time point) on **Cycle 1, Day 1** and **Cycle 1, Day 13** at the following timepoints:

- Predose
- Postdose
 - 30 minutes, 1, and 2 hours (± 15 minutes)
 - 3, 4, 6, 8, 12, and 14 hours (± 30 minutes)
 - 24 hours (± 1 hour)

In addition, if a patient presents with a potentially drug-related Grade ≥ 3 TEAE (e.g., rash, mucositis, diarrhea, pneumonitis), PK blood samples will be collected as soon as possible following the onset of the AE, and the time of the last dose and the time of blood draw should be recorded.

Phase 2: All patients will have blood samples drawn predose and at 1 hour and 2 hours (± 15 min) postdose for sparse PK sampling and time-matched concentration- ECG analysis on Day 1 of Cycle 1 and Day 1 of Cycle 2 for time-matched concentration- ECG analysis. In addition, if a patient presents with a potentially drug-related Grade ≥ 3 TEAE (e.g., rash, mucositis, diarrhea, pneumonitis), blood samples will be collected as soon as possible following the onset of the AE and the time of the last dose and the time of blood draw should be recorded. Blood samples will

also be collected predose on Cycle 3, Day 1 and every 8 weeks thereafter in order to correlate pozotinib concentrations with ctDNA and efficacy; the time of the last dose and the time of blood draw should be recorded.

5.4.9 Clinical Laboratory Tests

On Day 1 of each 28-day cycle, the patient's absolute neutrophil count (ANC) must be $\geq 1.5 \times 10^9/L$ and platelet count must be $\geq 100 \times 10^9/L$ before administering pozotinib. A local laboratory will be used to process all clinical specimens. The following clinical laboratory parameters will be evaluated in this study:

- **Complete Blood Count (CBC):** A CBC, including white blood cells (WBC), with 5-part differential, hemoglobin, and platelets will be performed at Screening, Day 1 of each cycle, and at the Safety Follow-up Visit. In addition, CBC will be done on Days 7 and 14 of Cycle 1 while the patient is in the hospital. The results of the laboratory assessments should be evaluated and medically accepted by the responsible physician before the start of each cycle. **If the Screening Visit is within 14 days of Day 1, the Day 1 CBC test is not required.**
- **Chemistry Panel:** A comprehensive chemistry and electrolytes, including blood urea nitrogen (BUN), AST/SGOT, ALT/SGPT, alkaline phosphatase (ALP), total bilirubin, albumin, calcium, lactate dehydrogenase, sodium, potassium, chloride, phosphate, magnesium, creatinine, glucose KL-6, and C-reactive protein, will be performed at Screening, Day 1 of each cycle, and at the Safety Follow-up Visit. **If the Screening Visit is within 14 days of Day 1, the Day 1 serum chemistry panel is not required.** In addition, a chemistry panel will be done on Days 7 and 14 of Cycle 1 while the patient is in the hospital.
- **Special note for the Day 1 sampling of each cycle:** If possible, blood samples should be drawn on **Day 1** of each cycle (prior to treatment); however, for logistical reasons, it is also acceptable to draw samples for assessment up to 7 days prior to the start of a cycle. The results of the laboratory assessments should be evaluated and medically accepted by the responsible physician before the start of each cycle.
- **Pregnancy Test:** A urine or plasma β -hCG test will be performed at Screening, Cycle 1, Day 1 (if the Screening pregnancy test was more than 7 days prior to Day 1), Day 1 of each cycle, and at the Safety Follow-up Visit for all women of childbearing potential.

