PHASE 1 SCHEDULE OF ASSESSMENTS AND PROCEDURES

Phase 1 Assessment	Screening	Treatment Period ^a (Each Cycle=28 [± 3] Days)						Safety Follow-up /End-of-Study Visit	Long-Term Follow-up Every 3 months After Discontinuation	
		Cycle 1				Cycle 2+				
	Day -30 to Day-1	Day				Day (± 2 days)		22	1	15
		1 7 13 14				Hospitalization				
Informed Consent	X									
Relevant Medical History	X									
Demographic Data	X									
Height and Weight ^b	X	X						X		X
Physical Examination ^c	X	X	X			X		X		X
Vital signs ^d	X	X	X			X		X		X
Resting O ₂ Saturation ^e	X	Daily						X		X
Pulmonary Function ^f	X	X	X			X		X		X
ECOG Performance Status ^g	X	X	X			X		X		X
Pregnancy Test ^h	X	X						X		X
Hepatitis B Surface Antigen Test ⁱ	X									
Hepatitis B Core Antibody Test ⁱ	X									
Hepatitis B Surface Antibody Test ⁱ	X									
Hepatitis C Antibody Test ^j	X									
HIV Antibody Test ^k	X									
Tumor Assessment ^l	X							X		X
Whole Blood (metabolic profile) ^m	X									
CBC with 5-part differential and platelets ⁿ	X	X	X			X		X		X
Serum Chemistry, including KL-6 and C-reactive protein ^o	X	X	X			X		X		X
Electrocardiogram ^p	X	X	X			X		X ^p		X
Echocardiogram or MUGA Scan ^q	X									
PK Blood Samples ^r		X		X						
Dispense Pozotinib ^s			Daily					X		
Dispense Supportive Care Medications, as needed			Daily					X		
Adverse Event Assessment ^t	X		Daily					X		X
Concomitant Medications	X	X	X			X		X		X
Patient Diary Dispensed/Collected						X		X		X

Phase 1 Assessment	Screening	Treatment Period ^a (Each Cycle=28 [\pm 3] Days)						Safety Follow-up /End-of-Study Visit	Long-Term Follow-up
		Cycle 1				Cycle 2+			
	Day -30 to Day-1	Day				Day (\pm 2 days)		35 (\pm 5) Days After Last Dose	Every 3 months After Discontinuation
		1	7	13	14	22	1		
		Hospitalization							
Telephone Contact ^a						x		x	x

- a) Patients must visit the site at the beginning of each cycle.
- b) Height only needs to be recorded during the Screening Visit.
- c) A complete physical examination, including auscultation, is required at Screening, Day 1 of each cycle, and at the Safety Follow-up Visit. Symptom-directed exams are required at other visits. In addition, a physical examination will be done on Days 7 and 14 of Cycle 1, while the patient is in the hospital.
- d) Vital signs will be measured at Screening, on Day 1 of each cycle, and at the Safety Follow-up Visit. In addition, vital signs will be measured on Days 7 and 14 of Cycle 1 while the patient is in the hospital.

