3.1.1 Phase 1: Dose-Finding

Phase 1 is a dose finding study with two parallel, randomized dose groups. Each group will undergo dose-finding scheme using a 3+3 design with the assessment of dose-limiting toxicities (DLTs) at up to three dose levels. Patients will be hospitalized for the first 2 weeks of Cycle 1.

- **Group 1 (once daily dosing [QD]):** Starting dose of 8 mg.
- **Group 2 (twice daily dosing [BID]):** Starting dose of 4 mg BID.

The DLT assessment will be conducted in Cycle 1 of the Phase 1 of the study. Pozotinib dose-finding will proceed based on the occurrence of DLTs during Cycle 1. Although DLTs will be evaluated based on the list of criteria specified below, toxicity related to the onset of any unexpected adverse events will be evaluated as well in addition to the DLTs. The MTD or MAD will be determined in each group independently. The DLTs for MTD/MAD will be assessed by the Medical Monitor in consultation with the site Principal Investigator. In addition to the defined DLTs, dose advancement/MTD will be decided based on all safety information, including adverse events that the subject experiences that are not defined as DLTs. A DLT will be any of the following treatment-related adverse events that occur during Cycle 1, despite optimal medical supportive therapy:

- **Non-Hematological Toxicity:**
 - Grade 3 or higher toxicity based on NCI-CTCAE (version 5.0), except for alopecia
 - Grade 3 or higher nausea and vomiting, despite treatment with oral anti-emetics at the highest dose
 - Grade 3 or higher diarrhea, despite diarrhea treatment at the highest dose
- **Hematological Toxicity:**
 - Grade 4 or higher neutropenia ($ANC < 0.5 \times 10^9/L$) sustained for 7 days or more
 - Febrile neutropenia ($ANC < 1.0 \times 10^9/L$ with a single temperature of $> 38.3^\circ\text{C}$ (101.0°F) or a sustained temperature of $\geq 38^\circ\text{C}$ (100.4°F) for more than one hour)
 - Neutropenic infection: Grade 3 or higher infection accompanying Grade 4 neutropenia ($ANC < 0.5 \times 10^9/L$) (requiring IV antibiotic, antifungal or antiviral agent administration/ requiring radiation or surgical therapy)
 - Grade 4 thrombocytopenia ($PLT < 25,000/\text{mm}^3$) or any grade thrombocytopenia requiring platelet transfusion

However, in case of $ANC < 0.5 \times 10^9/L$, conduct a repeat test on at least the 7th day in order to verify if it is lasted for 7 days or more.

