7 SAFETY ASSESSMENT

7.1 Safety Measures

It is the responsibility of the Principal Investigator to oversee the safety of the patients and to report all AEs/SAEs that are observed or reported during the study, regardless of relationship to study drug or clinical significance.

All patients taking study drug will be subject to DLT assessments, but patients in Phase 2 are unlikely to have DLTs, given that the dose of drug they are taking, is below the MTD determined in Phase 1.

The investigator together with the Sponsor's Medical Monitor will review all safety information per patient at each dose-finding meeting.

Safety data will also be reviewed on a regular basis by Spectrum's study monitoring team, which includes a Clinical Research Associate (CRA), Clinical Trial Manager (CTM), Medical Monitor, and other personnel from the company or its designee.

Adverse events will be characterized by intensity (severity), causality, and seriousness by the Investigator based on the regulatory definitions included below.

This study will utilize the National Cancer Institute (NCI) Common Terminology Criteria for Adverse Events (CTCAE) Scale Version 5.0 for AE grading.

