- s) Pozotinib will be dispensed on Day 1 of each cycle. Pozotinib should be taken with food and a glass of water (approximately 240 mL) at approximately the same time(s) each day.
- t) During the Screening Period, only SAEs will be recorded. All AEs will be collected from Cycle 1, Day 1 through the Safety Follow-up Visit. Patients will be hospitalized during the first 2 weeks of the study and will be monitored for safety assessments including AEs, vital signs, ECGs on Day 7 and Day 14 of Cycle 1. Adverse events will be assessed daily while hospitalized.
- u) Telephone contact for AE and concomitant medication assessment on Cycle 1, Day 22 (± 2 days), weekly during Cycle 2 and then Day 15 (± 2 days) in subsequent cycles. During the long-term follow-up patients will be contacted every 3 months to assess survival.

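### Asymptomatic laboratory DLTs are only partly ascertained on Days 15–28 of the Phase 1 DLT window, so DLT counts could be biased low

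*Combined protocol and SAP*

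**What the plan says.** Section 3.1.1 sets the window: "A DLT will be any of the following treatment-related adverse events that occur during Cycle 1". The schedule gives the cycle length as "Each Cycle=28 [± 3] Days". Three of the listed DLTs can be pure laboratory findings: Grade 4 neutropenia lasting at least 7 days, Grade 4 thrombocytopenia, and any non-hematological toxicity of Grade 3 or above other than alopecia. The last, as worded, takes in chemistry values and has no duration rule.

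For blood sampling, Section 5.4.9 states that "CBC will be done on Days 7 and 14 of Cycle 1 while the patient is in the hospital" and that "a chemistry panel will be done on Days 7 and 14 of Cycle 1 while the patient is in the hospital". Section 5.3.3 and Appendix 1 footnotes n and o agree. The Day 1 sample is waived if Screening was within 14 days. The next scheduled sample is the one for Cycle 2, Day 1, for which Section 5.4.9 adds that "it is also acceptable to draw samples for assessment up to 7 days prior to the start of a cycle". Between Day 14 and that sample, Section 5.3.6 and Appendix 1 footnote u provide one telephone call, on Day 22 (± 2 days), covering adverse events and concomitant medication.

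If an ANC below 0.5 × 10⁹/L has been seen, Section 3.1.1 asks the site to "conduct a repeat test on at least the 7th day in order to verify if it is lasted for 7 days or more". Section 5.3.4 keeps a patient in hospital after Day 14 if an evaluation is not passed, and only the failed evaluations are repeated.

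**The concern.** The window in which DLTs count and the schedule that measures laboratory DLTs do not match. A patient with normal blood on Day 14 has no scheduled CBC or chemistry for the next 8 to 15 days, and the telephone call cannot reveal an abnormality without symptoms. If the pre-Cycle 2 sample is taken early, it closes the blood record before the window closes. An abnormality arising later is first looked for at the pre-Cycle 3 sample, because the Cycle 2 contacts in Section 5.3.6 are also by telephone.

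The MTD/MAD is the Phase 1 primary endpoint and is decided on at most 6 patients per dose level. A laboratory DLT that is never measured is scored as no DLT. The possible error therefore runs one way: lower DLT counts and easier escalation.

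**Working it through.** **Plan's own figure.** 2 dosing groups × 3 dose levels × 6 patients = 36, which matches Section 8.1. It is not in dispute.

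**Gap between draws.** With a 28-day cycle, Cycle 2 Day 1 is study Day 29. The 7-day allowance puts the draw between 29 − 7 = Day 22 and Day 29.
- Gap after Day 14: 22 − 14 = 8 days to 29 − 14 = 15 days.
- With the ±3-day cycle window, Cycle 2 Day 1 falls on Days 26–32 and the draw on Days 19–32, so the gap is 5 to 18 days.
- A Day 22 draw leaves Days 23–28 (6 days) unsampled. The next scheduled sample is then the pre-Cycle 3 draw, nominally Day 50 to Day 57 (29 + 28 = 57; 57 − 7 = 50).

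**Share of episodes missed.** Assumptions: the abnormality is asymptomatic, its onset day t is uniform over the 14 days from Day 15 to Day 28, and it lasts L days. A single draw on day d sees it if t ≤ d ≤ t + L − 1. Share missed = 1 − (number of onset days seen)/14.

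| Episode length L | Draw Day 22 | Draw Day 28 | Draw Day 29 |
|---|---|---|---|
| 3 days | 11/14 = 79% | 11/14 = 79% | 12/14 = 86% |
| 7 days | 7/14 = 50% | 7/14 = 50% | 8/14 = 57% |
| 14 days | 6/14 = 43% | 0/14 = 0% | 1/14 = 7% |

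For example, with L = 14 and d = 22, onsets on Days 15–22 are seen (8) and onsets on Days 23–28 are missed (6).

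**Grade 4 neutropenia of exactly 7 days lying wholly within Days 15–28.** There are 8 possible onset days (15–22). The draw overlaps 7 of 8 if taken on Day 22, 4 of 8 on Day 25, 1 of 8 on Day 28 and 0 of 8 on Day 29. Overlap alone does not establish a 7-day duration; the repeat test is still needed.

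**Two draws, Day 22 plus Day 28 or 29.**
- Longest nominal gap: 8 days.
- 7-day episodes missed: 1/14 = 7% with either pair.
- 14-day episodes missed: 0% with either pair.
- 3-day episodes missed: 8/14 = 57% (Days 22 and 28) or 9/14 = 64% (Days 22 and 29).
- Wholly contained 7-day neutropenia: 7 of 8 onset days overlap a draw.

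**What under-counting would do to one escalation decision (illustration).** The dose-finding diagram is not shown, so the standard 3+3 rule is assumed: P(escalate) = (1 − q)³ + 3q(1 − q)⁵, with q = p(1 − f), where p is the true DLT rate and f the share of DLTs missed.
- p = 33%: f = 0 gives 0.434; f = 10% gives q = 0.297 and 0.500.
- p = 20%: f = 0 gives 0.709; f = 10% gives q = 0.18 and 0.752.

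Both p and f are assumptions. The documents give no value for f.

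**The case against.** A reader might infer that laboratory DLTs cannot be derived at all after Day 14. The documents do not support that. The pre-Cycle 2 draw can itself fall inside the window, and ANC and platelet thresholds must be met before Cycle 2 dosing. Patients who fail a discharge evaluation stay in hospital and have it repeated. Febrile neutropenia, neutropenic infection and thrombocytopenia needing transfusion should present clinically.

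The percentages are also open to challenge. They condition on late, asymptomatic onset, whose frequency is unknown. Fixed lengths of 3 or 7 days are assumptions. Dosing is continuous, and Cycle 1 allows neither dose modification nor growth factors, so longer episodes, which a late draw mostly sees, are plausible. A claim that every 7-day neutropenia is missed would be true only for a Day 29 draw. Some of the missed 7-day onsets (Days 23–28) reach their seventh day only after Day 28, so they would not meet the neutropenia rule within Cycle 1.

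On impact, Section 3.1.1 bases dose advancement on the whole safety record, not on the DLT count alone. The DLTs that Section 1.2 describes from the earlier Phase 1 studies were diarrhea and decreased appetite.

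These points limit the size of the concern but do not remove it. The repeat ANC test needs a first low value, the discharge rule acts only on what is abnormal by Day 14, and the wider safety record cannot contain a value that was not measured. The earlier studies were in Korean patients, and Section 1.2 says that BID dosing has not been investigated before.

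**Conclusion.** The point holds as one of partial ascertainment. Asymptomatic laboratory DLTs on Days 15–28 are sampled once, 8 to 15 days after Day 14 on the nominal schedule, and an early draw leaves up to the last 6 days of the nominal window unsampled. Under uniform onset, the single draw misses half or more of 7-day episodes and about four-fifths or more of 3-day episodes. For persistent (14-day) episodes, the draw date decides the matter: 43% missed on Day 22 against 0–7% on Day 28/29.

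It is tempting to conclude that the MTD/MAD therefore rests on incomplete DLT counts. That is not shown: the share of DLTs that are late and laboratory-only is not in the documents, and the escalation figures above only show the direction and what would follow if it were, say, 10%.

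Nor does the Phase 2 schedule bear on this point, since Phase 2 starts after the MTD/MAD is determined. What remains there is a wording conflict: Section 7.1 says that "All patients taking study drug will be subject to DLT assessments", while Section 3.1.1 places DLT assessment in Cycle 1 of Phase 1.

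**What to change.** 1. In Section 5.4.9 and Appendix 1 footnotes n and o (and the same footnotes in the synopsis schedule), remove the 7-days-early allowance for the first pre-Cycle 2 CBC and chemistry in Phase 1 patients. The sample is then taken at the end of the DLT window, on Day 28/29 before the Cycle 2 dose. The allowance can stay for later cycles. The cost is lost scheduling flexibility: results must be reviewed before Cycle 2 starts, although a local laboratory is already used.

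2. Optionally, add a CBC and chemistry around Day 22. Item 1 alone helps with persistent abnormalities; it does not help with short ones, and it sees fewer 7-day neutropenias that resolve within the cycle (0–1 of 8 onset days, against 7 of 8 with a Day 22 draw). The two draws together cover both, apart from brief episodes. The cost is real: a telephone contact becomes an attendance for a blood draw, in at most about 36 patients, some of whom may live far from the site.

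3. Reconcile Sections 3.1.1 and 5.4.9 on how a low count found at the end of Cycle 1 and confirmed in early Cycle 2 is classified. Which classification to adopt is for the sponsor and investigators.

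4. Reconcile the Section 7.1 sentence on DLT assessment of all patients with Section 3.1.1. Items 3 and 4 cost only text.

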5.4.10 Hepatitis B, Hepatitis C, and HIV Tests

Tests will be for hepatitis B surface antigens and hepatitis B core and surface antibodies. If the hepatitis B surface antigen test is positive, the patient will be excluded from the study. If only the hepatitis B core antibody and/or hepatitis B surface antibody is positive, a serum hepatitis HBV DNA test will be done. If this test is positive the patient is excluded from the study.

If hepatitis C antibody test is positive, an HCV RNA test will be done. If this test is positive, the patient is excluded from the study.

Whole blood sample is used for the HIV test. If this test is positive the patient is excluded from the study.

5.4.11 Electrocardiogram

A 12-lead ECG will be performed at Screening, predose and at 1 hour and 2 hours (± 15 min) postdose on Cycle 1, Day 1 and Cycle 2, Day 1 for time-matched concentration-ECG analysis, and at the patient's Safety Follow-up Visit. For Phase 1 patients, ECG will be performed predose on Days 7 and 14 of Cycle 1 while the patient is in the hospital. All ECGs will be sent for central analysis.

5.4.12 Cardiac Ejection Fraction

Cardiac ejection fraction will be assessed by either echocardiogram or multi-gated acquisition (MUGA) scan at Screening, and the Investigator can order subsequent tests based on patient standard of care. Results within 6 months prior to Cycle 1, Day 1 is acceptable if there is no major known cardiac event during this period.

5.4.13 Concomitant Medications

All medications administered from Screening to the Safety Follow-up Visit will be recorded on the CRF. A concomitant medication is any medication a patient is using from Cycle 1, Day 1 to the Safety Follow-up Visit. Pozotinib is not considered a concomitant medication.

All concomitant medications recorded at study entry must have a related, ongoing concomitant illness listed under the medical history at the time of patient entry into the trial. Patients may continue to use any ongoing medications not prohibited by the protocol.

All prescription and over-the-counter medications at trial entry as well as any new medications started during the trial must be documented on the CRF and in the source documents. The documentation should continue until 35 (± 5) days after the last dose of pozotinib.

Premedications (such as antiemetics) used for supportive care are allowed as per institutional standards or guidelines and Investigator discretion.

Other supportive and palliative therapies may be allowed during the study upon prior authorization from Sponsor's Medical Monitor.

